4.1.2 Handling of Missing Data

4.1.2.1 Seizure Data

If a patient withdraws during the time after which they have taken their first dose in the OLE, then seizure frequencies will be calculated from all the available data prior to the patient withdrawing.

Last observation carried forward (LOCF) methodologies that will be carried out on seizure data are discussed in Section 4.5.9.

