4.5.9 Seizure Data

The seizure frequency (per 28 days) and percentage change from baseline for total seizures, drop seizures and convulsive seizures during the study will be evaluated for each of the following 12 week periods:

- Week 1 (Day 1) to Week 12 (Day 84)
- Week 13 (Day 85) to Week 24 (Day 168)
- Week 25 (Day 169) to Week 36 (Day 252)
- Week 37 (Day 253) to Week 48 (Day 336)
- Week 49 (Day 337) to Week 60 (Day 420)
- Week 61 (Day 421) to Week 72 (Day 504)
- Week 73 (Day 505) to Week 84 (Day 588)
- Week 85 (Day 589) to Week 96 (Day 672)
- And so on for each 12-week interval

Please note that drop seizures are recorded for LGS patients only.

The percentage change from the baseline period each of the above periods will be presented, including for the last 12 weeks (Section 4.1.4.3).

Percentage change from the baseline period will be calculated as:

$$\left(\frac{\text{Frequency during the individual period} - \text{frequency during baseline period in core study}}{\text{frequency during baseline period in core study}} \right) \times 100$$

In this study, seizures are recorded on a weekly basis whereas in all core studies, seizures are recorded on a daily basis. Caregivers/patients are expected to call the IVRS system to record the frequencies of seizure subtypes experienced every 7 days from Visit 1 (Day 1) until the end of their participation. The frequency during each of the periods mentioned above will be based on 28-day averages and will be calculated as:

$$\text{Average number of seizures per day in the period} \times 28$$

All calls that take place during the period in question will contribute to the calculation of the average number of seizures per day in that period.

The average number of seizures per day in the period will be calculated as the average of:

$$\frac{\text{Number of seizures reported}}{\text{Number of days since last call}}$$

The number of days since the last call will be calculated as follows, and is dependent on whether the call took place <7, 7 or >7 days after the previous call (or after the date of Visit 1 (Day 1) in the case of the first call in the first period):

- If the call takes place exactly 7 days after the previous call, then the number of days since the last call will be 7.
- If the call takes place <7 days after the previous call, then the number of days since the last call will be calculated as:

$$(\text{Date of current call} - \text{date of previous call}) + 1$$

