- If the call takes place >7 days after the previous call, then the number of days since the last call will be 7.

For the seizure types and periods listed above, summary statistics will be presented for raw seizure frequencies and percentage change from baseline from core study baseline period. In addition, the number of patients with $\geq 25\%$, $\geq 50\%$, $\geq 75\%$ and 100% reduction in seizure frequency will be presented.

Furthermore, the percentage change from the core study baseline period will be presented for convulsive seizures from Dravet patients only and for drop seizures for LGS patients only.

All outputs will be repeated with the inclusion of an LOCF imputation step, which is described in the following steps:

- If a patient has valid data for ≥ 1 consecutive periods from and inclusive of the first period but only missing periods thereafter, then imputation of the missing period(s) will be carried out using the last 12 weeks of valid data (see Section 4.1.4.3).
- If a patient has intermittent missing periods (i.e. ≥ 1 missing period that falls after a populated period 1 and before subsequent populated periods), then the missing period(s) will be imputed with the closest earlier non-missing period of data.
- If the patient has ≥ 1 consecutive periods of missing data from and inclusive of the first period then no imputation will occur and data from the patient will be excluded from any LOCF presentations.

Summaries related to seizures as presented in this section and subsequent sections will include patients from all core studies except GWEP1332 Part A, from which data will be listed only.

The seizure frequency (per 28 days) and percentage change from baseline for total seizures, drop seizures and convulsive seizures during the study will be evaluated for the periods described in Section 4.5.9 and for the following subgroups:

- Patients taking clobazam
- Patients not taking clobazam
- Core study actual treatment: GWP42003-P
- Core study actual treatment: Placebo
- Patients taking clobazam; core study actual treatment: GWP42003-P
- Patients not taking clobazam; core study actual treatment: GWP42003-P
- Patients taking clobazam; core study actual treatment: Placebo
- Patients not taking clobazam; core study actual treatment: Placebo
- Patients with data at Week 37 (Day 253) to Week 48 (Day 336) [^]
- Patients with data at Week 37 (Day 253) to Week 48 (Day 336); patients taking clobazam [^]

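### SAP 4.5.9 adds one day to the divisor only when IVRS calls are under 7 days apart, and the look-back is unstated, so early calls may be biased in either direction

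*SAP*

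**What the plan says.** SAP 4.5.9 derives seizure frequency per 28 days from IVRS calls. Each call contributes the seizures reported divided by the days since the last call. These ratios are averaged over the calls in a 12-week period and multiplied by 28. The divisor has three branches:

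- Early call: "If the call takes place <7 days after the previous call, then the number of days since the last call will be calculated as" the current call date minus the previous call date, plus 1.
- On-time call: "If the call takes place exactly 7 days after the previous call, then the number of days since the last call will be 7".
- Late call: "If the call takes place >7 days after the previous call, then the number of days since the last call will be 7".

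For the first call the gap runs from Visit 1: "or after the date of Visit 1 (Day 1) in the case of the first call in the first period".

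On what a report covers, the SAP says only that calls are expected "every 7 days from Visit 1 (Day 1) until the end of their participation". Protocol 9.1.12 says the telephone diary is completed weekly. Neither document gives the recall wording. Baseline was collected differently: "In this study, seizures are recorded on a weekly basis whereas in all core studies, seizures are recorded on a daily basis".

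On which calls count, SAP 4.5.9 says: "All calls that take place during the period in question will contribute to the calculation of the average number of seizures per day". For patients who withdraw, SAP 4.1.2.1 adds that "seizure frequencies will be calculated from all the available data prior to the patient withdrawing". SAP 4.1.4.3 ends the last-12-weeks window at the earliest of study completion or withdrawal, the last IVRS call, and the last dose date on the End of Treatment outcome page.

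**The concern.** The extra day is added only below 7 days, and no reason is given. A 6-day gap and a 7-day gap therefore share the divisor 7. The below-7 branch also does not fit either natural form of the IVRS question. A count since the last call covers d days. A count over the past week covers 7 days, which equals d+1 only at d=6.

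The derived rate feeds total, drop and convulsive seizure frequency, percentage change from baseline, the 25%, 50% and 75% responder counts, the LOCF repeats and the subgroup tables. Because baseline was recorded daily, a wrong divisor acts on the extension side of the comparison only and does not cancel.

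A second, smaller gap concerns the end of treatment. The last-12-weeks window has a cut-off, but the numbered 12-week periods have none for a completer who goes on to taper. Protocol 9.2.12 then limits the seizure diary to one entry just before the End of Taper Period visit and one just before Follow-up. Protocol 8.1.2 and Section 10 say instead that IVRS recording continues through the taper.

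**Working it through.** **Inputs.** The divisor rule is from SAP 4.5.9. For a gap of d days, D(d) = d+1 if d < 7 and 7 if d ≥ 7, so D(d) = min(7, d+1). The days covered by a report, W(d), are not in the documents, so four assumptions are shown.

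**Formula.** At a constant seizure rate, relative bias = W(d)/D(d) - 1.

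**Check on schedule.** There is no stated figure to reproduce. At one seizure a day and d = 7, the rule gives 28 × 7/7 = 28 per 28 days, as it should.

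**Bias per call.**

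| Gap d | Divisor | Since last call, capped at 7: W = min(d,7) | Always past 7 days: W = 7 | Both call dates, capped at 7: W = min(d+1,7) | Since last call, no cap: W = d |
|---|---|---|---|---|---|
| 3 | 4 | 3/4: -25% | 7/4: +75% | 0 | 3/4: -25% |
| 5 | 6 | 5/6: -16.7% | 7/6: +16.7% | 0 | 5/6: -16.7% |
| 6 | 7 | 6/7: -14.3% | 7/7: 0 | 0 | 6/7: -14.3% |
| 7 | 7 | 0 | 0 | 0 | 0 |
| 8 | 7 | 0 | 0 | 0 | 8/7: +14.3% |
| 14 | 7 | 0 | 0 | 0 | 14/7: +100% |

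**Effect on a 12-week period.** With 11 on-time calls and one 3-day call, the mean ratio relative to truth is:

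- since last call: (11 + 3/4)/12 - 1 = -2.1%;
- past 7 days: (11 + 7/4)/12 - 1 = +6.2%.

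**Effect on responder status, for a patient who calls every 5 days.**

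- Since last call: a true 40% reduction leaves 0.60 of baseline, displayed as 0.60 × 5/6 = 0.50. The patient counts as a 50% responder.
- Past 7 days: a true 50% reduction is displayed as 0.50 × 7/6 = 0.583, a 41.7% reduction. The patient does not count.

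A seizure-free period stays at zero whatever the divisor, so the +1 does not touch the 100% responder count.

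**Off-schedule calls need not cancel.** Alternating 6- and 8-day gaps give (6/7 + 8/7)/2 = 1, no bias, if reports cover the whole gap. If reports are capped at 7 days they give (6/7 + 7/7)/2 - 1 = -7.1%.

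**Weighting.** The SAP averages ratios without weights. In the 11-plus-1 example a 3-day call carries 1/12 = 8.3% of the weight. By days covered since the last call it would carry 3/(11 × 7 + 3) = 3/80 = 3.75%.

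**Calls after End of Treatment.** SAP 4.1.4.3 keeps them out of the last-12-weeks endpoint. It therefore also keeps them out of the LOCF step for trailing missing periods, which uses that window. SAP 4.1.2.1 covers patients who withdraw. Nothing equivalent covers the numbered periods for a completer who tapers.

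**The case against.** The best defence is that the three branches form one coherent rule: inclusive day counting, capped at a week. Adding 1 is the SAP's usual convention (4.1.3 for day numbers, 4.5.2 for adverse event timing, 4.5.8.13 for dosing days). It suits the first call, which runs from Visit 1: a Day 7 call spans 7 dates and gets 7. If every report includes both call dates up to 7 days, the rule is exact at every gap. This stands as a possibility, but neither document says so. In the other sections the +1 counts a single span. Here the intervals run back to back, so early calls would count the shared call date twice.

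A reader might also infer that late calls are badly inflated, by 100% at a 14-day gap. The documents do not support that as the main reading. The cap at 7 makes sense only if a report covers at most 7 days, and then every call with d ≥ 7 is unbiased. The inflation arises only if reports cover the whole gap without a cap, which is the least supported assumption.

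A reader might further infer that taper-period calls distort the end-of-study results. The cut-off in SAP 4.1.4.3 prevents that for the last-12-weeks endpoint and the LOCF that relies on it. Only patients who do not continue the product taper, and because the protocol conflicts with itself on IVRS recording during taper, the call gap there cannot be fixed. No size is therefore attached to this part.

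Finally, these are secondary, descriptive endpoints with no hypothesis test, so no error rate is at stake.

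**Conclusion.** The point holds, mainly for early calls. The rule as written is right under one look-back that neither document states. Under the two more natural readings it is wrong for some or all early calls, with opposite signs: understated by 1/(d+1) if reports cover the days since the last call, and overstated for d below 6 if they always cover the past 7 days. A single stray call moves a period rate by a few percent; a patient who regularly calls early can cross a responder threshold.

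The sizes assume a constant seizure rate and depend on the assumed look-back. Call timing is not in the documents, so neither the net direction nor the net size can be computed. It would be wrong to conclude that the rule favors the treatment or that a calculation error has been shown. On-time callers are unaffected under every reading. This should be fixed, but it does not threaten the primary safety objective.

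**What to change.** 1. Check the IVRS question wording and state it in SAP 4.5.9.
2. Set the divisor to the days each report covers: d if since the last call; min(d,7) if that is capped at 7 days; 7 if always the past 7 days. Drop the +1 unless the question includes both call dates.
3. Compute the period rate as 28 × total seizures reported / total days covered, so that a short-gap call does not weigh as much as a full week.
4. Apply the SAP 4.1.4.3 end-of-treatment cut-off to the numbered 12-week periods, or state that End of Taper and Follow-up calls are excluded from them.
5. Reconcile Protocol 8.1.2 and Section 10 with 9.2.12 on IVRS recording during the taper.

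The cost is one SAP paragraph and one derivation step after checking the IVRS wording, plus a protocol clarification for item 5. The downside is small changes in displayed frequencies for off-schedule callers.

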thirds of patients in the high dose group (1.0 mg/kg/day, $n = 36$) experienced $\geq 75\%$ reduction in weekly drop seizures after 4 weeks' stable dosing, compared with one quarter of patients in the low dose group (0.25 mg/kg/day, $n = 32$). Moreover, 22% of patients in the high dose group achieved drop seizure freedom compared with 6% of patients in the low dose group³⁴. In the second study, which compared 3 doses of clobazam with placebo, 78% of patients in the high dose group (1.0 mg/kg/day, $n = 49$) achieved a $\geq 50\%$ reduction in drop seizures after 12 weeks' stable dosing, compared with 32% of patients taking placebo ($n = 57$)³⁵. Eligible patients from both of these trials were then given the opportunity to continue receiving clobazam as adjunctive treatment for LGS in an OLE study^{36,37}. Of the patients who had a $\geq 50\%$ reduction in drop seizures after 3 months' continuing treatment, 86% maintained this degree of drop seizure reduction at Year 3, and 47% were drop seizure free³⁷. Following the results of the 2 randomized trials, clobazam (under the name Onfi) was later approved by the FDA in 2011 as add-on therapy for LGS patients aged 2 years and older.

Lamotrigine has been shown to reduce the frequency of all seizure types in LGS, with one third of patients receiving lamotrigine achieving a $> 50\%$ reduction at 16 weeks compared with 16% receiving placebo³⁸. Similarly, more than half of LGS patients taking lamotrigine experienced a $> 50\%$ reduction in seizures at 12 weeks when compared with placebo in a 2-period, within-patient crossover study³⁹. Lamotrigine can paradoxically worsen seizures in DS patients however⁴⁰ and all sodium channel blockers are best avoided in DS patients. Potassium bromide can be effective at controlling seizures in DS, with over half of patients achieving a $> 50\%$ reduction and 30% becoming seizure-free at 3 months⁴¹. However, this compound has no effect on focal and tonic seizures (hence it is not used in LGS) and any initial efficacy is often not maintained long term^{33,41}.

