3.3.2 Secondary Endpoints

All Patients:

- Change in quality of life as measured with Quality of Life in Childhood Epilepsy (QOLCE) if 18 years of age or younger, or Quality of Life in Epilepsy (QOLIE) if 19 years of age or older, relative to the pre-randomization baseline of the Core Study, if assessed during the Core Study.
- Change in Subject/Caregiver Global Impression of Change (S/CGIC), relative to the pre-randomization baseline of the Core Study.
- Change in adaptive behavior as measured with the Vineland Adaptive Behavior Scales, Second Edition (Vineland-II), relative to the pre-randomization baseline of the Core Study, if assessed during the Core Study.
- Change in the number of inpatient epilepsy-related hospitalizations (number of hospitalizations due to epilepsy in each 28-day period), relative to the pre-randomization baseline of the Core Study.
- Change in the use of rescue medication (number of days used in each 28-day period), relative to the pre-randomization baseline of the Core Study.
- Maintenance of seizure frequency reduction and freedom from seizures during the OLE study.
- Percentage change in the frequency of total seizures, relative to the pre-randomization baseline of the Core Study.
- Number of patients considered treatment responders, defined as those with a $\geq 25\%$, $\geq 50\%$, $\geq 75\%$, or 100% reduction in total seizures, relative to the pre-randomization baseline of the Core Study.
- Number of patients experiencing a $> 25\%$ worsening, $- 25$ to $+ 25\%$ no change, 25 – 50% improvement, 50 – 75% improvement or $> 75\%$ improvement in total seizures, relative to the pre-randomization baseline of the Core Study.
- Percentage change in the frequencies of subtypes of seizures, relative to the pre-randomization baseline of the Core Study.
- Changes in duration of seizure subtypes as assessed by the Subject/Caregiver Global Impression of Change in Seizure Duration (S/CGICSD), relative to the pre-randomization baseline of the Core Study.
- Change in the number of episodes of status epilepticus, relative to the pre-randomization baseline of the Core Study.
- Change in cognitive function as measured with a cognitive assessment battery, relative to the pre-randomization baseline of the Core Study, if assessed during the Core Study.

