Table Number	Title	Analysis Set
Table 9.5.7.1	Summary of Drop Seizure Frequency - Patients with Week 37 to 48 Data	Safety Analysis Set
Table 9.5.7.2	Summary of Convulsive Seizure Frequency - Patients with Week 37 to 48 Data	Safety Analysis Set
Table 9.5.7.3	Summary of Drop Seizure Frequency - Patients Taking Clobazam - Patients with Week 37 to 48 Data	Safety Analysis Set
Table 9.5.7.4	Summary of Drop Seizure Frequency - Patients Not Taking Clobazam - Patients with Week 37 to 48 Data	Safety Analysis Set
Table 9.5.7.5	Summary of Convulsive Seizure Frequency - Patients Taking Clobazam - Patients with Week 37 to 48 Data	Safety Analysis Set
Table 9.5.7.6	Summary of Convulsive Seizure Frequency - Patients Not Taking Clobazam - Patients with Week 37 to 48 Data	Safety Analysis Set
Table 9.7.1	Summary of Responder Rates for Total Seizure Frequency	Safety Analysis Set
Table 9.7.2	Summary of Responder Rates for Total Seizure Frequency (LOCF)	Safety Analysis Set
Table 9.7.3	Summary of Responder Rates for Drop Seizure Frequency	Safety Analysis Set
Table 9.7.4	Summary of Responder Rates for Drop Seizure Frequency (LOCF)	Safety Analysis Set
Table 9.7.5	Summary of Responder Rates for Convulsive Seizure Frequency	Safety Analysis Set
Table 9.7.6	Summary of Responder Rates for Convulsive Seizure Frequency (LOCF)	Safety Analysis Set
Table 9.15.1.1	Summary of Quality of Life in Childhood Epilepsy Scores (2-18 Years)	Safety Analysis Set
Table 9.15.2	Summary of Quality of Life in Epilepsy Scores (19 Years and Above)	Safety Analysis Set
Table 9.16.1.1	Summary of the Vineland-II Adaptive Behavior Subdomain, Domain and Composite Scores	Safety Analysis Set
Table 9.16.1.2	Summary of the Vineland-II Adaptive Behavior Subdomain, Domain and Composite Adaptive Levels	Safety Analysis Set
Table 9.16.2.1	Summary of the Vineland-II Maladaptive Behavior Subdomain and Index Scores	Safety Analysis Set
Table 9.16.2.2	Summary of the Vineland-II Maladaptive Behavior Subdomain and Index Adaptive Levels	Safety Analysis Set
Table 9.17.1	Summary of Cognitive Assessment Battery Patient Measures	Safety Analysis Set
Table 9.17.2.1	Summary of Cognitive Assessment Battery Parent Measures - Executive (Behavior Rating Inventory of Executive Function)	Safety Analysis Set
Table 9.17.2.2	Summary of Cognitive Assessment Battery Parent Measures - Attention (ADHD Checklist)	Safety Analysis Set
Table 9.17.2.3	Summary of Cognitive Assessment Battery Parent Measures - Mood/Anxiety (BASC-2)	Safety Analysis Set

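### Maintenance of seizure reduction and seizure freedom is kept as a secondary endpoint, but every planned seizure output is a separate per-period summary and none follows the patients who responded, so turnover among responders is invisible.

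*SAP*

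**What the plan says.** SAP 3.3.2 lists "Maintenance of seizure frequency reduction and freedom from seizures during the OLE study" as an endpoint of its own, beside percentage change and the responder counts. The same item is an objective in SAP 2.2. SAP 4.7 names the protocol endpoints that will not be analysed, and this one is not among them.

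No SAP section says how maintenance is measured. Section 4.5.9 states that seizure frequency and percentage change "during the study will be evaluated for each of the following 12 week periods". Percentage change is also shown "including for the last 12 weeks (Section 4.1.4.3"). For each period, "summary statistics will be presented for raw seizure frequencies and percentage change from baseline from core study baseline period", and the numbers of patients reaching a 25%, 50%, 75% or 100% "reduction in seizure frequency will be presented". The outputs are repeated with LOCF. Subgroups are set by clobazam use, core-study treatment and having data in Weeks 37-48.

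Table 12 in Appendix 5 matches this. Tables 9.7.1 to 9.7.6 give responder rates for total, drop and convulsive seizures, observed and LOCF (for example "Summary of Responder Rates for Drop Seizure Frequency"). The Week 37-48 tables (9.5.7.x) cover frequency only. Protocol 13.6.3 adds only that the secondary endpoints are summarised descriptively over time.

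**The concern.** Maintenance is a question about patients: of those who achieved a reduction, how many kept it? Every planned output answers a different question, namely what share of patients met a threshold in a given period. If some responders lose their response and an equal number of others gain one, the table stays flat and will be read as maintained efficacy.

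Seizure freedom is the sharpest case. A constant small percentage seizure-free could be the same patients throughout or different patients each time.

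The protocol's background (3.1) shows the kind of measure that would answer the question. It reports, from an open-label extension of clobazam in LGS, that of the patients with at least a 50% reduction at 3 months, "86% maintained this degree of drop seizure reduction at Year 3". Nothing in Table 12 gives the corresponding figure for this trial.

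**Working it through.** The documents give no maintenance figure and no sample size calculation, so there is nothing to reproduce. The check is whether the planned tables can separate full retention from heavy loss. Responder, loss and dropout rates below are assumptions; the documents give none.

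**1. Fixed cohort, two periods.** Let p be the responder rate in both periods, r the share of earlier responders still responding, and c the share of earlier non-responders who convert. A flat rate requires p = p·r + (1 − p)·c, so c = p(1 − r)/(1 − p). Since c cannot exceed 1, the lowest possible r is max(0, (2p − 1)/p).

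| Flat rate p | c needed for r = 1/3 | Lowest possible r |
|---|---|---|
| 20% | 0.20 × 0.667 / 0.80 = 16.7% | 0% |
| 30% | 0.30 × 0.667 / 0.70 = 28.6% | 0% |
| 40% | 0.40 × 0.667 / 0.60 = 44.4% | 0% |
| 50% | 0.50 × 0.667 / 0.50 = 66.7% | 0% |
| 60% | 0.60 × 0.667 / 0.40 = 100% | 33% |
| 70% | impossible | 57% |
| 80% | impossible | 75% |

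For seizure freedom at an assumed 5%, complete replacement (r = 0) needs only 0.05/0.95 = 5.3% of the others to become seizure-free.

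**2. In patient numbers.** SAP Table 1 gives 171 + 225 = 396 randomised LGS patients, used here only for scale. At a flat 50% the planned table shows 198/396 in both periods. With full retention, 198/198 = 100% of responders are kept. With one-third retention, 66/198 = 33% are kept and 132 new responders take the others' place.

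**3. Eight periods, Weeks 1-12 to Weeks 85-96 (seven transitions).** Hold the rate at 45% and let a share L of responders lose response per period. The matching gain is L × 0.45/0.55. First-period responders who are responders in the eighth period: 0.45 + 0.55 × (1 − L/0.55)^7. Responders in every period, among first-period responders: (1 − L)^7.

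| L | Responding in period 8 | Responding in every period |
|---|---|---|
| 0% | 100% | 100% |
| 5% | 73% | 70% |
| 15% | 51% | 32% |
| 25% | 46% | 13% |

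All four rows give the same planned table: 45% in every period.

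**4. Attrition.** Suppose no patient changes status, non-responders leave at 10% per period and responders at 3%. After seven periods the observed rate is 45 × 0.97^7 / (45 × 0.97^7 + 55 × 0.90^7) = 36.4/62.7 = 58%. Under the LOCF rule each patient keeps the last status, so the LOCF responder tables stay at 45%. The artefact disappears there.

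LOCF has its own blind spot. Take 300 patients with 150 responders; 100 responders leave while responding and 100 non-responders leave. Observed: 50/100 = 50%. LOCF: 150/300 = 50%. Share of first-period responders still on study and responding: 50/150 = 33%. The LOCF rule also makes no exception for patients who finish as planned, although the footnote to SAP Table 2 says some end treatment after one year and others after two or more.

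**The case against.** The strongest reply is that this is a descriptive safety study, the protocol defines no maintenance measure, and the group's course over time is a reasonable reading of the word. That reading is tenable and limits how serious the gap is. It does not remove it: the endpoint is listed separately from the per-period percentage change and responder counts, and as planned it adds nothing to them.

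Four stronger readings are tempting, and the documents do not support them.

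- A reader might infer that responder percentages are the only evidence planned. They are not: frequency, percentage change, last-12-weeks, LOCF and Week 37-48 outputs are planned, and SAP 4.4.2 adds withdrawals by 12-week period. None follows responders: the Week 37-48 cohort is chosen on having data, and the withdrawal counts are split by indication and core study, not by response.
- A reader might infer that selective dropout will inflate the reported rates unnoticed. The documents give no withdrawal data by response status, and comparing observed with LOCF tables would expose this effect.
- A reader might infer that the trial could never yield a retention figure. Listing 9.2 holds patient-level derived seizure data, so one could be computed later; it is simply not pre-specified.
- A reader might treat the 86% as a benchmark. It is background on another drug, and the protocol does not say how withdrawals were counted.

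It is also fair to object that selecting patients on one period invites regression to the mean. That stands, and shapes the fix.

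**Conclusion.** The concern holds as a gap in pre-specification: a retained secondary endpoint has no within-patient analysis, and the planned summaries cannot distinguish retention from turnover. How far retention and the flat rate can diverge depends on that rate. In a fixed cohort, one-third retention is compatible with any assumed flat rate up to 60% and is impossible above it; the conversion required rises from 16.7% at a 20% rate to 100% at 60%. The conclusion does not depend on differential dropout. The primary safety endpoint is unaffected, so this should be corrected but does not threaten the main purpose of the trial.

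**What to change.** Add a definition of maintenance to SAP 4.5.9, by indication, using convulsive seizures for DS and drop seizures for LGS.

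- **Anchor:** patients with at least a 50% reduction in Weeks 1-12, and separately those with 100%. Repeat with Weeks 13-24 as anchor, because Weeks 1-12 include the 2-week titration.
- **For each later period, number and percentage who:** still respond; have lost response; have withdrawn (counted as not maintained); or ended the OLE as planned (removed from the denominator).
- **Beside it:** the number of anchor-period non-responders who gained response, and the number responding in every period.
- **If time to loss of response is shown:** count withdrawal as loss, censor at planned completion, and add a version that requires two consecutive periods without response, so that one noisy period is not taken as permanent loss.

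State with the table that choosing responders on a single period lets regression to the mean lower apparent retention, so the losses must be read together with the gains.

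The cost is a few descriptive tables from data already derived for Listing 9.2, with no new data and no hypothesis test. The maintenance figure may look less favourable than the per-period rates.

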13.1 Sample Size, Power and Significance Levels

As this is an open label safety study, there is no formal sample size calculation. All patients who wish to continue on IMP from the populations included in the double-blind Phase 2 and Phase 3 Core Studies in DS and LGS will be eligible for inclusion. Approximately 680 patients will be enrolled.

All data collected during this study will be summarized across time, using appropriate descriptive statistical methods. There will be no formal hypothesis testing.

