4.5 Safety and Efficacy Analysis

The safety of GWP42003-P is the primary endpoint and the aim of this study is to evaluate long term safety and tolerability and as such, there will be no formal hypothesis testing. Endpoints will be summarized as detailed in the following sections.

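### No responder table counts early withdrawal as non-response, and the observed-data tables state no denominator, so by-period responder rates can overstate the share of treated patients still responding on drug

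*SAP*

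**What the plan says.** SAP Section 4.1.2.1 provides that when a patient withdraws after the first OLE dose, "seizure frequencies will be calculated from all the available data prior to the patient withdrawing". Section 4.5.9 divides follow-up into 12-week periods and adds each patient's last 12 weeks. It says that the number of patients with at least 25%, 50%, 75% and 100% "reduction in seizure frequency will be presented".

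All outputs are then repeated with LOCF. For a patient whose later periods are all missing, "imputation of the missing period(s) will be carried out using the last 12 weeks of valid data". Section 4.1.4.3 ends that window at the earliest of completion or withdrawal, last IVRS call and last dose, so the carried value is an on-drug value. A patient with no first-period data is left out of the LOCF outputs.

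Appendix 5 lists Tables 9.7.1 to 9.7.6, for example "Summary of Responder Rates for Total Seizure Frequency" and "Summary of Responder Rates for Drop Seizure Frequency", each without and with LOCF. No denominator is given for the non-LOCF percentages. Section 4.5.1 names the safety analysis set in general terms, and Section 4.5.9 leaves GWEP1332 Part A out of the seizure summaries. By contrast, Section 4.5.2 states a denominator for time of AE onset, and Section 4.6.1 states one for the behavior survey.

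**The concern.** Maintenance of seizure reduction during the extension is a secondary objective (SAP Section 2.2). A reader of a late-period responder rate will probably want to know what share of treated patients are still responding on the drug. A patient who has withdrawn is no longer doing so, whatever the last diary entries showed.

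If the observed tables use patients with data, withdrawn patients simply leave the calculation. Under LOCF, a responder withdrawn for an AE, or under the mandatory liver criteria in Protocol Section 10, remains a responder in every later period. The protocol allows 208 weeks, which is 208 / 12 = 17.3, or seventeen full 12-week periods. One early value could therefore fill most of a patient's record. For this question both versions lie at or above the answer, so showing them side by side does not bracket it.

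**Working it through.** There is no planned figure to reproduce. The plan states no responder or withdrawal rate, says that "there is no formal sample size calculation" (Protocol Section 13.1), and tests nothing.

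**Inputs, all assumed, for one period before anyone completes by design**
- w, share of treated patients withdrawn before the period: 10% to 40%.
- pS, response rate in those remaining: 50%.
- pW, response rate in the withdrawn patients' last 12 weeks: 0%, 20% or 50%.

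**Formulas**
- Withdrawal counted as non-response: (1 − w) × pS.
- Observed-data rate, if the denominator is patients with data: pS. Excess: w × pS.
- LOCF rate, if every withdrawn patient has first-period data: (1 − w) × pS + w × pW. Excess: w × pW.

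Neither excess can be negative. Neither formula requires withdrawal to be related to response.

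**Results in percent, with the excess in points in brackets**

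| w | Withdrawal as non-response | Observed | LOCF, pW = 0 | LOCF, pW = 20% | LOCF, pW = 50% |
|---|---|---|---|---|---|
| 10% | 45 | 50 (5) | 45 (0) | 47 (2) | 50 (5) |
| 20% | 40 | 50 (10) | 40 (0) | 44 (4) | 50 (10) |
| 30% | 35 | 50 (15) | 35 (0) | 41 (6) | 50 (15) |
| 40% | 30 | 50 (20) | 30 (0) | 38 (8) | 50 (20) |

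Example at w = 30% and pW = 20%: 0.70 × 0.50 = 35%; adding 0.30 × 0.20 = 6 points gives 41% under LOCF.

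**If the denominator were the whole safety set.** The non-LOCF rate would be 0.70 × 0.50 = 35% at w = 30%, with no excess. After the first completions, however, completers would also count as failures. Suppose half the patients are missing, 80% of those have completed, and pS = 50%. The rate would be 0.50 × 0.50 = 25%. Removing completers and counting only withdrawals as failures gives 0.25 / (0.50 + 0.50 × 0.20) = 41.7%.

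**Limit on the remedy.** Removing completers while keeping every withdrawal can mislead in the other direction. Of 100 patients, suppose 30 have withdrawn, 60 have completed and 10 remain, 5 of them responding. The rate would be 5 / (30 + 10) = 12.5%, mainly because completers leave the denominator and withdrawals do not.

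**The case against.** Several objections have force.

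- **LOCF carries non-response too.** A reader might infer that withdrawn patients are never counted as non-responders. That is not so: under LOCF the share 1 − pW of them are, which is 80% at pW = 20%. If most withdrawn patients were not responding at the end, LOCF lies close to the withdrawal-as-failure rate.
- **The denominator is not stated.** A reader might conclude that withdrawn patients are definitely dropped from the observed tables. The SAP does not say so, and its general safety-set rule could be read the other way. This stands as a correction, but it also means that two programmers could produce different rates.
- **Not every rate is affected in this way.** The last-12-weeks rate uses each patient's own final window and keeps withdrawn patients who have data.
- **Attrition is reported.** Section 4.4.2 tabulates withdrawals by 12-week period, indication and core study, and Table 1.2 gives reasons. This helps, but it is not tied to responder status. At best a reader could approximate the missing rate for early periods, and only if the responder tables print the number with data. After completions begin, the LOCF tables mix withdrawn and completed patients.
- **The reasons for leaving are unknown.** Protocol Section 10 does not list lack of effect as a withdrawal criterion. The point does not depend on it.
- **The stakes are limited.** These are secondary endpoints in a safety study where "there will be no formal hypothesis testing". No error rate or power is affected.

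**Conclusion.** The point holds in a limited form. No responder table treats early withdrawal itself as non-response, and the observed-data tables leave their denominator open. For the share of treated patients still responding on drug, the observed rate (if based on patients with data) and the LOCF rate can only equal or exceed the withdrawal-as-failure rate.

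With 50% response in those remaining and 10–40% withdrawn, the observed excess is 5–20 points. The LOCF excess ranges from 0 to 20 points, depending on how withdrawn patients were doing in their last window. All these rates are assumptions, because the documents give none.

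It would go too far to say that every responder rate in the plan is optimistic. The LOCF excess is zero when pW = 0, the observed excess disappears under a full safety-set denominator, and the last-12-weeks rate does not lose withdrawn patients from its denominator. The gap should be closed because a long-term extension will be read for sustained response, but it is a matter of description, not of inference.

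**What to change.** 1. In SAP Section 4.5.9, state that the denominator for Tables 9.7.1, 9.7.3 and 9.7.5 is patients with data in the period, and print that number.
2. Add one sensitivity version of each of these three tables for the four 12-week periods through Week 48. SAP Table 2 shows that some patients finish by design at about one year, so these periods come before any planned completion. Safety-set patients (less GWEP1332 Part A) who withdrew early stay in the denominator as non-responders for every period after withdrawal. Show the number withdrawn beside the rate.
3. For periods after Week 48, show this version only among patients whose scheduled treatment end falls after the period. Apply the restriction equally to withdrawn and continuing patients. The SAP must define scheduled end per patient first, because it depends on country (SAP Section 3.1.3) and on the commercial-availability rule (Protocol Section 4.1). Where it cannot be determined, stop at Week 48.

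The cost is three more tables and a less favourable rate in print. Through Week 48 they need only diary and disposition data already collected; later periods also need the scheduled end date.
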